2.6 Theory of change

The goal and the objectives of the project are based on the following theory of change (**Figure 4**).

Figure 4: DYNAMIC project theory of change

3 STUDY DESIGN

The primary intervention (i.e. ePOCT+ implementation) study will be conducted in two phases, with the study design detailed below and summarized in **Figure 5**.

3.1 Phase 1: cluster randomized controlled study in 40 health facilities

The ePOCT+ tool, as well as the complementary training and supervision tools, will be provided to HCWs of 20 of the 40 selected PHC facilities (intervention arm) in Morogoro and Mbeya regions, while the other 20 HF will serve as controls (control arm), using a cluster randomized controlled study design. Randomization (1:1) of HFs will be done by region and HF type. Sick children aged 1 day to 14 years will be managed in accordance with the study arm to which the HF they attend has been assigned. The comparator for phase 1 will be routine care as currently implemented in Tanzania (see Section 8.1.5 for more detail). To assess the primary and secondary outcomes, final decision on referral, diagnoses and treatments at initial consultation will be recorded by HCWs electronically; children will also be followed-up by a phone call to their caregiver at day 7 to determine their final health status. Due to the pragmatic nature of the study, the design is adaptive in nature, where changes to the implementation may be incorporated throughout the study to account for issues

encountered in monitoring data and feedback from the field. These changes apply to the implementation context and exclude significant adaptations of the algorithm.

[figure not shown]
The purpose of Phase 1 is to compare the effect of using ePOCT+ with routine case management of sick children on the rational prescription of antibiotics, while ensuring a favorable clinical outcome. To date, a prior version of the ePOCT tool was assessed in conditions closer to that of an explanatory trial (Keitel et al., 2017). The present study is designed as a pragmatic randomized controlled study to assess the safety and impact on antibiotic prescriptions of implementing ePOCT+ (including its associated POC tests), supported by initial and continuous training and targeted supervision of health workers, in children attending Tanzanian primary health care facilities. The study will be implemented in settings of targeted future use and involving routine health care personnel, and include all sick children (except those coming for a follow-up visit in the context of a chronic condition). ePOCT+ provides support to HCWs in managing these sick children. Since the intervention takes place at the health provider level and that their practices are influenced by the context of the HF they are working in, randomization at HF level rather than at HCW level or at individual patient level was chosen.

3.2 Phase 2: scale-up of the intervention to 100 health facilities and transformation into a dynamic algorithm

The ePOCT+ tool will be extended to the 20 HFs serving as controls in Phase 1, as well as up to 60 additional neighboring facilities of our target area, to reach a total of up to 100 facilities (around 60 in Morogoro and 40 in Mbeya). In Phase 2, an adaptive study design will be used measuring the same outcome indicators as in Phase 1. The medical content of the algorithm will no longer be static, but rather modifiable according to the local data captured by ePOCT+ during Phase 1. Each modification will be designed and evaluated by the clinical expert group for its coherence, safety and potential benefit. Modifications in the algorithms designed to perform as well as the original algorithm but using fewer/different resources will be implemented in the facilities they were designed to serve (for example, if certain facilities do not have access to a certain resource). Similarly, modifications designed to personalize the algorithm according to demographic characteristics, geography or season will be implemented on the target population for which they were intended. Modifications of ePOCT+ aimed at improving health outcomes of subgroups of patients (for example those with respiratory infections) will be implemented in a sub-study where patients are randomized at an individual level. Modifications confirmed as safe and useful will then be implemented, while the non-beneficial changes will not be retained.

Examples of algorithm modifications expected to have positive impacts that will be explored for implementation are: 1) adapting the frequency of malaria testing in areas with very low endemicity; 2) improving the accuracy of pneumonia diagnosis, including , including through the use of novel POC diagnostic tools; 3) assessing the utility of using dengue rapid tests if an outbreak occurs; 4) or typhoid rapid tests in areas of high prevalence; 5) improving the prediction of severe disease; 6) improving the algorithm for malnourished or HIV positive children and; 7) testing sick children for sickle cell disease.

Figure 5: Study design overview.

3.3 Syndromic surveillance enhanced by microbiological testing

The syndromic surveillance (i.e. based on the clinical data generated by the use of ePOCT+) will be enhanced by microbiological surveillance in a few sentinel HFs, as well as in any facility according to abnormal data patterns detected by ML (based on predefined clinically supervised thresholds) to identify potential outbreaks or endemic diseases requiring specific attention.

Three to four HFs in each study district (6 to 8 in total) will be selected to play the role of sentinel sites, representative of different epidemiological conditions. In these HFs, blood, stool, urine or nasopharyngeal samples will be regularly collected from targeted sub-groups of children at risk of diseases of specific interest for surveillance (e.g. watery diarrhea to detect cholera or unspecific fever to detect dengue). In these sentinel sites, when attending a child presenting with one of the syndromes of interest (based on the data entered in the ePOCT+ tablet), the HCW will automatically see an additional screen requesting to collect the necessary additional sample (e.g. stool in case of diarrhea or blood in case of unspecific fever), if the patient has provided informed consent for that.

If a child presents a syndrome of specific interest for surveillance (e.g. fever and rash) due to pathogens that cannot be detected based on a day 0 sample only (e.g. *Rickettsiosia* or *Leptospira*), he/she would be asked to return to the facility at day 7 or later and provide an additional sample. In such rare cases, the child would most likely not be cured at day 7 and would need to return to the facility for further care anyway. If the result turns out to be positive for one of these pathogens, the child will be proposed specific treatment if necessary (see chapter 8.1.3).

In addition to sentinel sites, machine learning anomaly detection will be developed to visualize spatiotemporal clusters of events, which aims to help clinicians detect disease outbreaks (e.g. fever combined with abdominal tenderness in a cluster of households may be indicative of an outbreak of typhoid or another intestinal pathogen). The use of additional available spatiotemporal data sources will be explored in further developing the surveillance platform based on well-known risk factors of

diseases in the area that are prone to outbreaks. For example, remotely sensed data from satellite imagery may be incorporated to monitor environmental conditions (e.g. land surface temperature, rainfall, vegetation cover) known to influence seasonal patterns of some diseases. Likewise, information about the locations of water and sanitation features can be incorporated to help identify areas that are at increased risk of waterborne or water-related diseases. In response to the spatiotemporal analyses, at a later stage of the surveillance study, we may expand surveillance sample collection beyond the sentinel sites using a mobile surveillance team.

3.4 Mixed-methods operational research

Throughout Phases 1 and 2, as well as during the last year of the project, mixed-methods studies will be conducted in HFs and communities, as well as at district and national levels, to understand the contextual factors that facilitate or impede the implementation, sustainability and scale-up of digital health interventions such as ePOCT+ in PHC settings. Examples of such factors may include socioeconomic and ecological profiles of communities, working conditions of the clinicians in the HFs, among others.

3.4.1 Cross-sectional quality of care surveys

Before the start of phase 1, during the second half of phase 1, and around 6 months after the beginning of phase 2, three cross-sectional surveys in a subset of randomly selected HFs will be performed to assess the quality of the consultation done by HCWs and their level of compliance to the algorithm (and thus to guidelines). Among the 40 HF included in Phase 1, 18 HF (10 in Morogoro and 8 in Mbeya, half of them being intervention HF and the other half control HF) will be randomly selected. Observers will be trained to attend and observe (without interfering) 25 consecutive consultations with children aged 1 day to 14 years per HF, thus a total 450 HCW/child pairs. Changes over time will be assessed during the three cross-sectional surveys. Before-and-after intervention analysis will be performed between the baseline analysis and the phase 1 intervention arm HF, as well as between the control arm HF in phase 1 and those same HF that will then use the ePOCT+ tool in Phase 2. For the 9 intervention HF, this will provide another way (besides data recorded through the ePOCT+ tool) to measure potential improvement in the quality of the consultation over time. The tools for the quality of care surveys can be found in **Appendix 1**.

3.4.2 In-depth interviews, focus group discussions and surveys with health care workers

Interviewees (health providers) will be selected through a mix of purposive and random sampling. Based on the data collected through the medAL-monitor tool, we will select health facilities based on relevant criteria such as levels of uptake of and compliance with the algorithm. Within the health facilities, providers will be randomly selected among those available on that day.

Interviews will be conducted using a semi-structured interview guide developed for the study. The questionnaire will cover several themes, such as 1) experience using the ePOCT+ tool, 2) management of tablets in the facility, 3) training on the content and use of the algorithm, 4) experience with the e-learning modules and the supervision and mentorship tool (medAL-monitor).

For each question, probes will be used to generate further explanations from study participants. Each interview will be conducted as an informal discussion with open questions, leaving room for the HCW to express additional elements. In order to reduce study bias, participants will be strongly encouraged to be as open as possible in expressing their opinion and reassured on full confidentiality. The tools for the interviews and focus groups can be found in **Appendix 2**.

To complement the qualitative data, we will quantitatively evaluate the impact of using the ePOCT+ tool and the additional training and mentorship provided through the project on clinicians' competencies and confidence in their skills and decisions in Phase 1. The initial 3-day training will be implemented with a pre- and post- test administered to the participants. The e-learning platform will also come with short tests at the end of each module for the learners to self-assess their

understanding of the content. Lastly, baseline and end-line assessments and surveys will be used to compare intervention and control facilities. Similar assessment tools will be used in Phase 2, except a control group will not be available for comparing the difference in clinical competencies between baseline and end-line.

3.4.3 Caregiver and patient exit interviews

Structured exit interviews will be conducted with caregivers of sick children (as well as potentially older children aged 9-14 years) who attended HFs that are part of the study. A purposive sampling method will be used to select a wide range of children treated for different pathologies at participating HFs. Face-to-face interviews will be conducted using a semi-structure questionnaire. Themes that will be explored include: 1) quality of care received; 2) influence of the tablet on the interaction between clinician and patient/caregiver, 3) Confidence in treatment and management using ePOCT+ and 4) Impact of the use of ePOCT+ on future health seeking behavior. The questionnaires are adapted from the Service Provision Assessment (SPA) sick child client exit interviews (USAID et al. The Demographic and Health Surveys Program), a methodology recommended by the WHO. The tools for the exit interviews can be found in **Appendix 2**.

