1.4 Monitoring and evaluation of health interventions

Currently the planning, budget allocation, monitoring, and evaluation of health interventions is largely based on reports of data aggregated at the facility level, called MTUHA in Tanzania, and managed in the DHIS2 platform used by the majority of African countries. Data aggregation at the facility is done manually on paper forms or excel tables using paper records that are supposed to be filled by HF personnel on a daily basis. Since the filling of these registries is additional work on top of patient care, registries are often incomplete and may be filled in retrospectively (Wilms et al. 2014). Even if HCWs are motivated to report correct data, they lack the tools to make correct diagnoses. As a result, prevalence of many conditions that require diagnostic tools that are often out of stock or not available altogether, is falsely represented in DHIS2. For example, bacterial pneumonia is constantly over-diagnosed as diagnostic tests to distinguish bacterial from viral respiratory infections are not available. Furthermore, the manual data aggregation at the facility level and entry process into DHIS2 is error prone. In sum, the data available for health management and reporting is of insufficient quality (Mghamba et al. 2004, Farnham et al. 2020).

Misdiagnoses have consequences that reach beyond the patient. They increase re-attendance rates, further congesting PHC clinics and accruing economic losses not only for families but for the entire health system. Systematic errors in patient-level data accumulate, and as they are aggregated in DHIS2 to measure population-level indicators, they have the potential to bias the statistics used to prioritize public health interventions and, importantly, identify epidemics.

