These measures or indicators include the evaluation of the effects of the use of ePOCT+ (versus routine care in Phase 1; over time and across geographical areas in Phase 2) for managing sick children aged under 15 years presenting to PHC facilities on:

Unscheduled secondary consultations:

- % of children with one or more unscheduled re-attendance visits at any HF by day 7

Severe outcome by day 7:

- % of children with non-referred secondary hospitalization by day 7
- % of children who have died by day 7

Primary referrals:

- % of children referred to hospital or admitted to inpatient ward at a health centre at initial consultation
- % of children who were hospitalized among those referred (i.e. referral completed)

Appropriate case management for malaria at initial consultation

- % of febrile children tested for malaria
- % of malaria positive children prescribed an antimalarial
- % of malaria negative children prescribed an antimalarial
- % of untested children prescribed an antimalarial

Appropriate case management for other conditions at initial consultation

- % of key symptoms and signs checked and diagnostic tests performed by HCWs
- Distribution of final diagnoses (including their severity) made by HCWs
- Concordance between treatment prescribed and final diagnoses made by HCWs
- Concordance between final diagnoses as proposed by ePOCT+ and final diagnoses by HCW (*intervention HFs only*)

Definitions used for the outcome measures and indicators of objective 1

- Clinical cure is a positive answer to the question “Is the child cured?” OR “Has the child improved?” (if not cured) asked to caregiver through a phone call (or home visit) at day 7. Non-referred secondary hospitalizations (see definition below) will however be considered as clinical failures even if the child is already cured at day 7.
- Initial consultation is the first visit of a sick child for an acute problem at a HF participating in the study (and thus registered electronically); timeframe from completion of the initial visit up to midnight of the same day.
- Re-attendance visit is a consultation (not necessarily at a HF participating in the study) taking place from the day after initial consultation up to day 7 included. A re-attendance visit can be scheduled (proposed by the HCW on a certain day) or unscheduled (upon decision by caregivers).

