In both intervention and control facilities, it is assumed that usual diagnostic tests and treatments will be provided through the routine health care system. Control HFs will not receive additional POC tests that HFs in Tanzania would not normally have available in similar settings (i.e. CRP test). Care for children under the age of five years is free of charge while caregivers are expected to pay out of pocket for health care expenses of older children (unless expenses are covered under an insurance policy). However, when not available at the HF, patients must procure their medications from nearby pharmacies or other HFs. To allow testing of the intervention under conditions as close as possible to those expected for future implementation, we will not provide routine diagnostics or medications in either intervention or control facilities. However, we will ensure that immediate life-saving treatments are available and will support the facility staff in managing stocks through routine mechanisms.

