10.5 Analyses of data from operational research studies

Quantitative data from cross-sectional quality of care surveys, provider clinical competency or knowledge assessments, and caregiver and patient interviews will be analyzed using conventional statistical methods to compare means (t-tests or paired t-tests) or frequencies (chi-square tests) across intervention groups or time periods. Regression analysis may also be used to explore associations of multiple predictors with outcomes of interest.

All interviews and focus-group discussions will be audio-recorded with the participant's informed consent. Detailed notes will be taken during the interviews. Records will be manually transcribed in its original language (Kiswahili) and translated into English. A qualitative data analysis software (e.g. Nvivo) will be used to code the English interview transcripts in order to identify emerging themes. A predefined list of codes based on the interview guide and the recurrent themes highlighted in the detailed notes will be used. New codes will be created when new themes are identified during more detailed analysis of the transcripts. Deductive coding will be used to extract the themes based on the interview guide, but inductive coding will also be used to extract any unexpected themes that arise during the interviews.

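### Exit-interview caregivers are chosen purposively by the condition treated, which can depend on arm, so the t-tests and chi-square tests planned across arms or periods lack their stated meaning

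*Protocol*

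**What the plan says.** Protocol section 3.4.3 covers interviews with caregivers, and possibly older children, at facilities in the study. On selection it says: "A purposive sampling method will be used to select a wide range of children treated for different pathologies at participating HFs". It gives no number of interviews per facility or arm, no quota, and no rule to keep selection alike across arms. On content it says: "Themes that will be explored include: 1) quality of care received; 2) influence of the tablet on the interaction between clinician and patient/caregiver". Themes 3 and 4 concern confidence in management with ePOCT+ and its effect on later care seeking.

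Section 10.5 covers the quantitative data from the quality-of-care surveys, the provider assessments and the interviews: "caregiver and patient interviews will be analyzed using conventional statistical methods to compare means (t-tests or paired t-tests) or frequencies (chi-square tests) across intervention groups". The same tests may be used to compare periods. It adds: "Regression analysis may also be used to explore associations of multiple predictors with outcomes of interest". No covariates, weights or allowance for facility are named.

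The SAP covers only the medAL-mentor study and does not mention exit interviews.

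**The concern.** Purposive sampling is sound for gathering a range of views. A significance test between arms needs something more: the people compared must differ between arms only by chance and by the intervention. Randomization supplies that for all children who attend, or for a sample of them drawn without regard to anything that happens after randomization.

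Here the selection variable is the condition the child was treated for. It is fixed during the consultation that ePOCT+ is designed to change. Two caregivers chosen because their children carried the same label, one from each arm, may have had children who were ill in different ways. A comparison over time has the same weakness if ePOCT+ was introduced in between, as happens in the former control facilities.

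Caregiver perception is an Objective 5 indicator, and the mixed-methods work is meant to inform sustainability and scale-up. A difference in reported quality of care could arise from whom the study chose to interview, with no difference in the care given.

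**Working it through.** **1. The plan's own figure.** There is none. The documents state no sample size, power or expected difference for the exit interviews, so the check is of the text, followed by an illustration.

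**2. Does the label depend on arm?** Three places in the protocol suggest that it does.
- Section 7.1 lists as a secondary outcome, compared between arms in Phase 1: "Distribution of final diagnoses (including their severity) made by HCWs".
- Section 8.1.6 says that control facilities will not be given the CRP test. Table 2 gives CRP a role in children at risk of bacterial pneumonia.
- Section 1.4 says of routine data that "bacterial pneumonia is constantly over-diagnosed", because tests to separate bacterial from viral infection are lacking.

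**3. What selection on such a label can do.** All inputs here are assumed; none comes from the documents. There is no arm effect on satisfaction.
- Truly severe share of attending children: s = 0.10 or 0.20.
- Pneumonia label given to 90% of severe children in both arms, and to b = 50% (control) or 10% (ePOCT+) of mild children.
- Share of interviews drawn from labelled children: q = 0.25 or 0.50.
- Satisfaction 80% if mild, and 60% or 70% if severe.

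Severe share among those interviewed = q × 0.9s / [0.9s + b(1−s)] + (1−q) × 0.1s / [0.1s + (1−b)(1−s)].

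Largest case (s = 0.20, q = 0.50, satisfaction 60% v 80%):
- Control: 0.5 × 0.18/0.58 + 0.5 × 0.02/0.42 = 0.179, so satisfaction is 0.80 − 0.20 × 0.179 = 0.764.
- ePOCT+: 0.5 × 0.18/0.26 + 0.5 × 0.02/0.74 = 0.360, so satisfaction is 0.80 − 0.20 × 0.360 = 0.728.
- Spurious difference: −3.6 points.

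Smallest case (s = 0.10, q = 0.25, satisfaction 70% v 80%): severe shares are 0.058 and 0.134, and the difference is −0.10 × 0.076 = −0.8 points.

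Rejection rate of a nominal two-sided 5% test of two proportions (unpooled normal approximation, independent observations), over all eight combinations:

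| Interviews per arm (assumed) | Rejection with no arm effect |
|---|---|
| 100 | 5% to 9% |
| 225 | 6% to 14% |
| 450 | 6% to 24% |

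With consecutive sampling the severe share is s in both arms and the expected difference is zero, provided that the attending children are alike in the two arms.

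**4. Clustering.** Facilities are randomized, and section 10.5 names no adjustment for this. With design effect DE = 1 + (m−1) × ICC, the true level of a nominal 5% test is 2 × [1 − Φ(1.96/√DE)]. For assumed ICC 0.01 and m = 10 interviews per facility, DE = 1.09 and the level is 6%. For ICC 0.10 and m = 25, DE = 3.4 and the level is 29%. This is separate from the selection problem, and correcting it would not remove the selection problem.

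**The case against.** The strongest reply is that these interviews are mainly descriptive. Section 3.4.3 itself plans no comparison, whereas sections 3.4.1 and 3.4.2 do so explicitly for their own data. The Objective 5 indicator is perception of the intervention, which purposive sampling can serve. Section 10.5 limits the tests to quantitative data and sends recorded interviews to qualitative coding. Themes 3 and 4 name ePOCT+ and have no control-arm counterpart in Phase 1. Regression is also allowed.

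Much of this stands, and it narrows the point. The between-arm problem rests mainly on theme 1, quality of care received. It may extend to theme 2, since control facilities also use tablets. Which items control caregivers are asked depends on Appendix 2, which is not in the text reviewed. But section 10.5 names caregiver and patient interviews among the data to be tested, and the quantitative items come from the same selected caregivers. The regression is optional and exploratory, and adjusting for the health worker's diagnosis would condition on a post-randomization variable.

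A reader might infer more than the documents support:
- **That a difference will be reported as an ePOCT+ effect.** No section says so.
- **That interviewers know the arm when choosing whom to interview.** Section 3.4.3 does not say who selects or what they know.
- **That equal quotas per condition will be filled in both arms.** No quotas are stated.
- **That the bias favours ePOCT+.** In the illustration it runs against ePOCT+, and it would reverse if caregivers of severely ill children were the more satisfied.

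**Conclusion.** The point holds in a limited form. The sampling in section 3.4.3 does not support the tests in section 10.5, whether between arms or before and after ePOCT+. This follows from the text and from the protocol's own reasons for expecting diagnoses to differ by arm. It does not depend on the illustration.

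Its size and direction cannot be found from the documents. The 0.8 to 3.6 points, and the rejection rates up to 24%, rest wholly on assumed severity, labelling, satisfaction and interview numbers; at the low end the distortion is negligible. Only ancillary operational research is affected. The Phase 1 primary and secondary outcomes do not use these interviews. The change is worth making because it is cheap.

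**What to change.** Choose one of two routes.

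1. **If any exit-interview item is to be compared between arms or periods:** state in section 3.4.3 that caregivers for those items are selected by one rule, identical in all facilities and blind to diagnosis and treatment, such as consecutive or every k-th eligible child. Section 3.4.1 already observes 25 consecutive consultations in each randomly selected facility. State in section 10.5 that these comparisons allow for clustering by facility.
2. **If purposive sampling is kept throughout:** amend section 10.5 so that exit-interview data are reported descriptively, without between-arm or before-after tests.

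Either route takes a sentence or two. The first leaves rarer conditions less well represented in the compared items, and keeping a separate purposive sample for open-ended questions may need some additional interviews. The second costs nothing in the field but gives up formal comparison.
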